Dose cohort	A group of newly enrolled patients treated at a specific dose and regimen at the same time.
Dose level	The dose of drugs given to the patient.
Enrollment	Point/time of patient entry into the study; the point at which informed consent is obtained and patient meets all inclusion and none of the exclusion criteria.
Patient number	A unique identifier number (consisting of the center number and patient number) assigned to each patient who enrolls in the study.
Period	A subdivision of the study timeline; divides stages into smaller functional segments such as screening/baseline, treatment, washout, etc.
Phase II	Selected group of patients enrolled during the Phase II part of the study.
Stage in cancer	The extent of a cancer in the body. Staging is usually based on the size of the tumor, whether lymph nodes contain cancer, and whether the cancer has spread from the original site to other parts of the body
Stage related to study timeline	A major subdivision of the study timeline; begins and ends with major study milestones such as enrollment, completion of treatment, etc.
Study evaluation completion (SEC)	Point/time which marks the end of study for an individual patient. Survival continues beyond SEC.
Study treatment	Drugs whose properties are being tested in combination in the study (i.e. study drugs or study drugs combination).
Study treatment discontinuation	Point/time when patient permanently stops taking study treatment for any reason (i.e. end of treatment).
Variable	Identifier used in the data analysis; derived directly or indirectly from data collected using specified assessments at specified timepoints

Amendment 10

Amendment rationale

In 2018, LGX818 (encorafenib) 450 mg orally QD, in combination with MEK162 (binimetinib) 45 mg orally BID, received marketing approval in several jurisdictions, including the United States and the European Union, for the treatment of patients with unresectable or metastatic *BRAF* V600-mutant melanoma. This approval was based on the ongoing randomized Phase III COLUMBUS Study (CMEK162B2301).

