MEK162 is mainly metabolized by glucuronidation and is not a strong CYP3A4 inhibitor. *In vitro* data and some clinical data suggest MEK162 might have CYP3A4 induction potential. However, no significant PK exposure changes for LGX818 were observed in the LGX818 and MEK162 dual-combination phase up to date. Even if the induction occurs between MEK162 and LEE011, it will likely decrease LEE011 exposure and therefore will not pose a safety risk. Overall the PK drug-drug interaction between MEK162 and LEE011 is expected to be minor and not pose significant safety risk.

In this ongoing [CMEK162X2110] study, the PK profiles of LGX818 and MEK162 when given in combination were generally similar to those in their corresponding single agent studies. With increasing LGX818 doses (50mg, 100mg, 200mg, 400mg, 450mg and 600mg), the PK exposure of MEK162 did not change. These data indicated that no significant PK drug-drug interactions between LGX818 and MEK162 were observed.

For the safety of the study patients to be treated with the triple combination, the starting dose of LEE011 in the triple combination will include a 1/9 fraction of the single agent MTD of LEE011 (i.e. MTD 900 mg QD 3 week on/1 week off schedule), i.e 100 mg QD. For the starting dose of LGX818 and MEK162, the RP2D of 450mg QD and 45mg BID was selected as a well-tolerated dose from the ongoing CMEK162X2110 clinical study for the dual combination. Doses of LEE011 and possibly of LGX818 will be alternately escalated for each compound during dose escalation (see Section 6.2.3 and Section 6.2.4.2 for provisional dose levels and details on the dose escalation process). Furthermore, appropriate eligibility criteria and specific DLT criteria as well as specific dose modification and stopping rules are included in this protocol. Recommended guidelines for prophylactic or supportive treatment for expected toxicities are provided in Section 6.1.2 and Appendix 3. Specific safety assessments (i.e. post-dose ECGs/ triplicate ECGs) will be performed to monitor cardiac safety during triple-combination study treatment. The PKs of MEK162, LGX818 and LEE011 will also be assessed in the current study to further evaluate the potential for a PK drug-drug interaction.

2 Rationale

[Any language regarding the triple combination of LGX818/MEK162/LEE011 in this Section is not applicable to the USA and Singapore]

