6.3.2 Treatment interruption and treatment discontinuation

Each patient is only allowed a maximum of two dose reductions after which the patient will be discontinued from the study treatment. In addition, a patient should discontinue treatment with the LGX818 and MEK162 dual or LGX818 and MEK162 and LEE011 triple combination if, after treatment is resumed at a lower dose, the toxicity recurs with the same or worse severity. However, the patient may continue to receive study treatment at the next lower dose level, if appropriate, at the discretion of the Investigator and in discussion with the Sponsor. If, after interruption of treatment and resolution, treatment is resumed at the same dose following the criteria in [Table 6-4](#) and the same toxicity recurs with the same or worse severity, next treatment re-initiation must resume at the next lower dose level irrespective of duration. For each patient,

once a dose level reduction has occurred, the dose level may not be re-escalated during subsequent treatment cycles, except in cases where LGX818 dosing was reduced to 450mg QD during MEK162 dosing interruption.

Dose reduction for LGX818 and/or MEK162 and/or LEE011, as applicable means treatment at the next lower dose level of the respective study drug. For LGX818 and LEE011, this is the next lower previously tested dose level. For MEK162 this is the next lower dose level (please see [Table 6-1](#) and [Table 6-2](#)). If a patient requires a dose interruption of >21 days from the intended day of the next scheduled dose, then the patient must be discontinued from the study treatment unless the patient has experienced objective evidence of clinical benefit. If the patient has experienced objective evidence of clinical benefit, and in the opinion of the investigator it is in the best interest of the patient to remain on study, then following discussion with the sponsor, the patient may continue on study treatment.

Table 6-4 Criteria for interruption and re-initiation of LGX818/MEK162/LEE011 triple-combination treatment

Recommended Dose Modifications for (dual) LGX818 and MEK162 or (triple) LGX818 and MEK162 and LEE011 combination study treatment	
Worst Toxicity CTCAE v4.03 Grade (unless otherwise specified)^a	Recommended Dose Modifications any time during a cycle of therapy
No toxicity	Maintain dose level
Blood and lymphatic system disorders	
Anemia (Hemoglobin)	

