Grade 3 (PLT < 50 – 25 x 10 ⁹ /L)	Interrupt dosing of LGX818 and MEK162 (and LEE011 in patients treated in triple-combination arm) until resolved to ≤ Grade 1, then: - If resolved in ≤ 7 days, then maintain dose level of LGX818 and MEK162 (and LEE011 in patients treated in triple-combination arm). - If resolved in > 7 days and/or with signs of bleeding, then ↓ 1 dose level* of LGX818 and MEK162 (and LEE011 in patients treated in triple-combination arm)
Grade 4 (PLT < 25 x 10 ⁹ /L)	Discontinue patient from study drug treatment.

Recommended Dose Modifications for (dual) LGX818 and MEK162 or (triple) LGX818 and MEK162 and LEE011 combination study treatment	
Worst Toxicity CTCAE v4.03 Grade (unless otherwise specified)^a	Recommended Dose Modifications any time during a cycle of therapy
Gastrointestinal disorders	
Diarrhea	
Grade 1	Maintain dose level of LGX818 and MEK162 (and LEE011 in patients treated in triple-combination arm), but initiate anti-diarrhea treatment.
Grade 2	Interrupt dosing of LGX818 and MEK162 (and LEE011 in patients treated in triple-combination arm) until resolved to Grade ≤ 1 with proper therapy and monitoring and then maintain dose level of LGX818 and MEK162 (and LEE011 in patients treated in triple-combination arm) - For 2 nd occurrence of diarrhea Grade 2 within 15 days, interrupt dosing of LGX818 and MEK162 (and LEE011 if applicable) until resolved to Grade ≤ 1, then reduce MEK162 and LGX818 (and LEE011 in patients treated in triple-combination arm) by 1 dose level* and maintain dose level of LGX818 (and LEE011 in patients treated in triple-combination arm)
Grade 3	Interrupt dosing of LGX818 and MEK162 (and LEE011 in patients treated in triple-combination arm) until resolved to Grade ≤ 1, then reduce dose of LGX818 and MEK162 (and LEE011 in patients treated in triple-combination arm) by 1 dose level*.
Grade 4	Discontinue patient from study drug treatment.
Note: Anti-diarrhea medication is recommended at the first sign of abdominal cramping, loose stools or overt diarrhea.	
Nausea / Vomiting	
Grade 1	Maintain dose level of LGX818 and MEK162 (and LEE011 in patients treated in triple-combination arm)

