Grade 2	Interrupt dosing until recovery to G1 with proper therapy and monitoring – Re-initiate MEK162 and LGX818 (and LEE011 in patients treated in triple-combination arm) at same dose level – If recurs at G2, interrupt dosing of MEK162 and LGX818 (and LEE011 in patients treated in triple-combination arm) until recovery to G1 and then re-initiate at next lower dose level

Recommended Dose Modifications for (dual) LGX818 and MEK162 or (triple) LGX818 and MEK162 and LEE011 combination study treatment

Worst Toxicity CTCAE v4.03 Grade (unless otherwise specified)^a

Recommended Dose Modifications any time during a cycle of therapy

Nausea / Vomiting (continued)

Grade 3	Interrupt dosing of LGX818 and MEK162 (and LEE011 in patients treated in triple-combination arm), until resolved to Grade ≤ 1, then ↓ 1 dose level* of LGX818 and MEK162 (and LEE011 in patients treated in triple-combination arm)
Grade 4	Discontinue patient from study drug treatment.

Note: Interrupt dosing for ≥ grade 3 vomiting or nausea only if the vomiting or nausea cannot be controlled with optimal antiemetics (as per local practice).

Pancreatitis

Grade 1	Maintain dose level of LGX818 and MEK162 (and LEE011 in patients treated in triple-combination arm)
Grade 2	Interrupt dosing until recovery to G1 with proper therapy and monitoring – Re-initiate MEK162 and LGX818 (and LEE011 in patients treated in triple-combination arm) at same dose level – If recurs at G2, interrupt dosing of MEK162 and LGX818 (and LEE011 in patients treated in triple-combination arm) until recovery to G1 and then re-initiate at next lower dose level
Grade ≥3	Discontinue patient from study drug treatment.

Investigations (Renal)

Serum creatinine

Grade 1 (> ULN – 1.5 x ULN)	Maintain dose level of LGX818 and MEK162 (and LEE011 in patients treated in triple-combination arm)
Grade 2 (> 1.5 – 3.0 x ULN)	Interrupt dosing until recovery to G1 with proper therapy and monitoring – Re-initiate MEK162 and LGX818 (and LEE011 in patients treated in triple-combination arm) at same dose level – If recurs at G2, interrupt dosing of MEK162 and LGX818 (and LEE011 in patients treated in triple-combination arm) until recovery to G1 and then re-initiate at next lower dose level
Grade ≥3	Discontinue patient from study treatment.

Recommended Dose Modifications for (dual) LGX818 and MEK162 or (triple) LGX818 and MEK162 and LEE011 combination study treatment

Worst Toxicity CTCAE v4.03 Grade (unless otherwise specified)^a

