^d All patients with ALT or AST >5.0x ULN and total bilirubin > 1.5x ULN in the absence of cholestasis must immediately be withdrawn from study treatment and every attempt should be made to carry out the **liver event follow-up assessments** as described below in [Section 6.3.3](#).
If combined elevations of AST or ALT and total bilirubin do not meet the defined thresholds, please follow the instructions for isolated elevation of total bilirubin and isolated elevation of AST/ALT, and take a conservative action based on the degree of the elevations (e.g. discontinue treatment at the situation when omit dose is needed for one parameter and discontinue treatment is required for another parameter). After all elevations resolve to the defined thresholds that allow treatment re-initiation, re-start the treatment either at the same dose or at one dose lower if meeting a criterion for dose reduction

^e “Cholestasis” defined as: ALP elevation (>2.0 x ULN and R value (ALT/ALP in x ULN) ,2.0) in patients without bone metastasis, or elevation of ALP liver function in patients with bone metastasis.

^f All values refer to the average of triplicate measurements.

^g Ophthalmic monitoring mandated for retinal event, posterior uveitis, RVO: further evaluation with specialized retinal imaging (e.g. ocular coherence tomography, angiography).

^h Except: 1) lymphopenia unless clinically significant, 2) occurrence of KA and/or cutaneous SCC, 3) alkaline phosphatase, 4) AEs not considered clinically significant like alopecia study drug-related fever, electrolyte abnormalities (including K, NA, Cl, HCO₃, Mg, Ca, PO₄).

* ↓ 1 dose level refers to: next lower previously tested dose level of LGX818 and LEE011 and the next lower dose level of MEK162 (please see [Table 6-1](#) and [Table 6-2](#)).

Recommended Dose Modifications for (dual) LGX818 and MEK162 or (triple) LGX818 and MEK162 and LEE011 combination study treatment

**Worst Toxicity CTCAE v4.03 Grade
(unless otherwise specified)^a**

Recommended Dose Modifications any time during a cycle of therapy

** Confounding factors and/or alternative causes for increased transaminases should be excluded before dose interruption/reduction. They include but are not limited to: concomitant medications, herbal preparations or dietary supplements, infection, hepato-biliary disorder or obstruction, new or progressive liver metastasis, and alcohol intake.

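### Table 6-4 tells sites both to reduce and to maintain LGX818 (and LEE011 in triple-combination patients) after a second Grade 2 diarrhea within 15 days

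*Protocol*

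**What the plan says.** **Diarrhea, Grade 2 (Protocol Section 6.3.2, Table 6-4).** At a first episode all drugs are interrupted and restarted at the same dose. At a second episode within 15 days all drugs are interrupted until Grade 1 or better, and the cell continues: "then reduce MEK162 and LGX818 (and LEE011 in patients treated in triple-combination arm) by 1 dose level* and maintain dose level of LGX818". The words that follow apply the maintain instruction to LEE011 in triple-combination patients as well.

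**Footnote \* to Table 6-4.** A one-level reduction means the "next lower previously tested dose level of LGX818 and LEE011 and the next lower dose level of MEK162".

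**General rule (Section 6.3.2).** If treatment was resumed at the same dose and the same toxicity returns at the same or worse severity, "next treatment re-initiation must resume at the next lower dose level irrespective of duration". Also, "once a dose level reduction has occurred, the dose level may not be re-escalated during subsequent treatment cycles", with one exception: LGX818 lowered to 450 mg during a MEK162 interruption.

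**Neighbouring rows.** Grade 3 diarrhea: "then reduce dose of LGX818 and MEK162 (and LEE011 in patients treated in triple-combination arm) by 1 dose level", with no maintain clause. For Grade 2 recurrence of nausea/vomiting, pancreatitis and raised creatinine, the study drugs are interrupted "until recovery to G1 and then re-initiate at next lower dose level".

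**Retinal events, Grade 3 (triple combination).** The opening text restarts the study drugs one level lower. The bullet for resolution within 21 days lowers MEK162 and LGX818 but keeps LEE011 unchanged. Failure to resolve within 21 days means discontinuation.

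**The concern.** A site cannot lower and keep the dose of the same drug at the same restart. Whichever it does, it departs from half of the sentence, and Section 12 allows no authorized deviations.

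The trigger is foreseeable. Section 1.2.2.2.1 lists diarrhea among the frequent MEK162-related events, and Section 1.3.2 expects overlapping gastrointestinal toxicity when LEE011 is added. A site that reduces generally cannot go back. A site that maintains re-exposes a patient with recurrent toxicity to the full LGX818 (and LEE011) dose.

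Table 6-4 still governs dosing. Amendment 10 edited it for ILD/pneumonitis, TEN and QTcF, and its change list shows no correction to the diarrhea row. The stake is patient dosing and safety, including the dose-reduction and dose-intensity summaries of Section 10.5.2.4. It does not touch the efficacy rules.

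**Working it through.** The plan gives no figure to reproduce. The check is a comparison of texts, followed by simple arithmetic on the size of the dose difference.

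**Step 1: what each text does to each drug when treatment restarts**

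| Text (Section 6.3.2) | MEK162 | LGX818 | LEE011 (triple) |
|---|---|---|---|
| Diarrhea Grade 2, second episode: first half of sentence | reduce | reduce | reduce |
| Diarrhea Grade 2, second episode: second half | not mentioned | maintain | maintain |
| Diarrhea Grade 3 | reduce | reduce | reduce |
| Nausea/vomiting, pancreatitis, creatinine: Grade 2 recurrence | next lower level | next lower level | next lower level |
| General recurrence rule | next lower level; drugs not named | same | same |

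The conflict lies within one complete sentence of current text. Footnote \* defines the size of a step and does not say which drugs take it.

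**Step 2: which half fits the rest**

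- The general rule describes this sequence exactly: interruption, restart at the same dose, recurrence, then restart one level lower. It does not name the drugs. The Glossary defines study treatment as the study drugs or their combination, so reading it as all drugs is the better reading, though not a certain one.
- The Grade 3 diarrhea row and the comparable Grade 2 recurrence rows contain no maintain clause.

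The maintain clause is therefore the part that does not fit.

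**Step 3: size of the difference**

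Ratio = dose if reduced / dose if maintained = next lower level / current level.

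LGX818, using the doses listed in Section 1.3.2 (50, 100, 200, 400, 450, 600 mg):

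- 50/100 = 100/200 = 200/400 = 0.50
- 400/450 = 0.89
- 450/600 = 0.75

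The Amendment 4 rationale also mentions an 800 mg cohort: 600/800 = 0.75, inside the same range.

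LEE011: the levels actually tested are not stated. Assuming they are the provisional levels of Table 6-2 (50, 100, 200, 300, 400, 800, 900 mg):

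- 50/100 = 100/200 = 400/800 = 0.50
- 200/300 = 0.67
- 300/400 = 0.75
- 800/900 = 0.89

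MEK162 is reduced under either reading.

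**Step 4: who is exposed**

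The Amendment 10 rationale counts 5 dual + 5 triple = 10 patients on treatment. All 10 are potentially exposed to the diarrhea rule, and the 5 triple patients to the retinal rule. Current doses, and the number who will meet either trigger, are not given.

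**Step 5: retinal Grade 3 (secondary)**

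Resolution within 21 days leads to restart; no resolution leads to discontinuation. The only restart case therefore falls under both LEE011 instructions: lower with the other study drugs, and keep unchanged.

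**The case against.** **The general rule already settles it.** The recurrence rule is mandatory, whereas Table 6-4 is headed as recommended modifications and Section 6.3.1 says the dose may be adjusted. On that view the maintain clause is only untidy. This helps show which half is wrong, but the rule does not name the drugs. A site working from the table still meets an instruction it cannot follow.

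**The wrong half might be deleted.** Section 1.3.1 ties gastrointestinal toxicity, diarrhea included, specifically to MEK162. The CPK rows (symptomatic Grade 3, and Grade 4) and the edema Grade 3 row lower MEK162 alone. A MEK162-only rule would be coherent for LGX818. But the same list in Section 1.3.1 covers nausea/vomiting and retinal toxicity, for which Table 6-4 does lower LGX818, and Grade 3 diarrhea itself lowers every drug. The list therefore does not decide the matter. What stands is that the intended direction is probable, not proven, and the sponsor should confirm it.

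**The size is overstated.** The two dual-combination RP2Ds use LGX818 450 or 600 mg, and the triple combination starts at 450 mg. From those doses the ratio is 0.89 or 0.75. The 0.50 end needs a patient now at 100, 200 or 400 mg, and none is documented. This is fair: 0.50 is a bound.

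**The retinal point is weak and incomplete.** A specific bullet can be read as overriding a general opening sentence. That is reasonable, but the text does not say so. The Grade 2 retinal row has a similar LEE011 mismatch: unchanged if unresolved at 21 days, reduced if symptoms persist beyond 7 days. Any repair should cover both rows.

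**Conclusion.** The concern holds. The Grade 2 diarrhea cell gives opposite orders for LGX818, and for LEE011 in triple-combination patients. It is a live dosing rule and should be fixed.

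Confidence that the contradiction exists is high. That reduction is intended is the better-supported reading, resting on the general recurrence rule and the neighbouring rows, but it is not certain.

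The LGX818 range of 0.50 to 0.89 depends on the dose a patient is taking now. The LEE011 range, also 0.50 to 0.89, additionally assumes that every provisional level was tested. At most 10 patients are exposed to the diarrhea rule and at most 5 to the secondary retinal Grade 3 conflict, which is also real on the text. No efficacy analysis or sample-size figure is affected.

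**What to change.** In Table 6-4, Diarrhea Grade 2, delete the closing clause that maintains LGX818 (and LEE011 in triple-combination patients). All study drugs then restart one level lower after a second episode within 15 days, in line with the general recurrence rule and the neighbouring rows. The sponsor should confirm this intent when issuing the change.

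In the retinal Grade 3 row keep a single LEE011 instruction, and check the Grade 2 retinal row at the same time.

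The cost is a clarification letter or minor amendment, with no added visits or procedures.

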Eye disorders- any other	CTCAE Grade 3 for > 14 consecutive days
	CTCAE Grade 4
Gastrointestinal disorders	Diarrhea CTCAE Grade $\geq 3 \geq 48$ hrs, despite the use of optimal anti-diarrhea therapy
	Nausea or vomiting CTCAE Grade $\geq 3 \geq 48$ hrs, despite the use of optimal anti-emetic therapy
	Pancreatitis CTCAE Grade ≥ 3
Investigations (Renal)	Serum creatinine CTCAE Grade ≥ 3
Investigations (Hepatic) ^c	Blood bilirubin (total bilirubin) CTCAE Grade ≥ 3
	AST or ALT CTCAE Grade ≥ 3 in conjunction with blood (total) bilirubin CTCAE Grade ≥ 2 of any duration
	AST or ALT CTCAE Grade 3 for > 7 consecutive days
	AST or ALT CTCAE Grade 4.
	Serum alkaline phosphatase CTCAE Grade 4 > 7 consecutive days

Toxicity	Any of the following criteria:
Investigations (Metabolic)	Serum lipase and/or serum amylase (asymptomatic) CTCAE Grade 3 > 7 consecutive days
	Serum lipase and/or serum amylase (asymptomatic) CTCAE Grade 4
Cardiac disorders	≥ CTCAE Grade 3
Investigations (Cardiac)	Serum CK/CPK CTCAE Grade 3 for > 14 consecutive days if clinically significant (symptomatic)
	Serum CK/CPK CTCAE Grade 4 for > 14 consecutive days
	QTcF interval ≥ 501 ms on at least two separate ECGs (only for triple combination)
Vascular disorders	Persistent hypertension CTCAE Grade ≥ 3 requiring more than one drug or more intensive therapy than previously
General disorders and administration site conditions	Fatigue CTCAE Grade 3 for > 7 consecutive days
	Edema CTCAE grade 3 for > 14 consecutive days
Other Adverse Events ^d	Any other CTCAE Grade ≥ 3 toxicity (except SCC ^e)

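### For nausea and vomiting controlled by antiemetics, Table 6-4 recommends a hold at Grade 2 but waives it at Grade 3, and its note overlaps the Grade 4 stopping rule

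*Protocol*

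**What the plan says.** Table 6-4 sets out the recommended dose modifications. For nausea and vomiting its rows are:

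- **Grade 1:** keep the dose.
- **Grade 2, first occurrence:** "Interrupt dosing until recovery to G1 with proper therapy and monitoring", then restart all study drugs at the same dose.
- **Grade 2, recurrence:** hold all study drugs "until recovery to G1 and then re-initiate at next lower dose level".
- **Grade 3:** hold all study drugs "until resolved to Grade ≤ 1, then ↓ 1 dose level* of LGX818 and MEK162" (and LEE011 in the triple arm).
- **Grade 4:** "Discontinue patient from study drug treatment".

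The note below these rows reads: "Interrupt dosing for ≥ grade 3 vomiting or nausea only if the vomiting or nausea cannot be controlled with optimal antiemetics".

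The text of Section 6.3.2 adds two general rules. If treatment is resumed at the same dose after an interruption and the toxicity recurs at the same or worse severity, "next treatment re-initiation must resume at the next lower dose level irrespective of duration". And "Each patient is only allowed a maximum of two dose reductions", after which treatment ends. A reduction may not be reversed, except where LGX818 was lowered to 450 mg during a MEK162 interruption.

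Table 6-3 (Section 6.2.5) counts nausea or vomiting as dose-limiting only at Grade 3 or above for at least 48 hours, "despite the use of optimal anti-emetic therapy".

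**The concern.** A dose-modification table should ask for at least as much caution at a higher grade as at a lower one. Here the antiemetic exemption starts at Grade 3 and skips Grade 2. A site that follows the table stops all drugs for a controlled Grade 2 event and has no hold to apply for a controlled Grade 3 event. If the Grade 2 event recurs, the patient loses a dose level that cannot normally be regained and moves one step closer to the limit on reductions.

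Two further ambiguities follow from the note. It does not say whether waiving the Grade 3 hold also waives the dose reduction that the row places after it, so two sites could dose the same patient differently. And its lower bound reaches into Grade 4, where the row gives a stopping rule with no condition attached.

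**Working it through.** The plan states no figure to reproduce. The check sets the rows and the note side by side for an event that optimal antiemetics control.

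| Grade | Row | Effect of note | Holds per event |
|---|---|---|---|
| 1 | Keep dose | Not covered | 0 |
| 2, first | Hold, restart at same dose | Not covered | 1 |
| 2, recurrence | Hold, restart one level lower | Not covered | 1 |
| 3 | Hold, then one level lower | Hold waived | 0 |
| 4 | Discontinue | Overlaps in wording | Row has no hold step |

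**Holds.** Two successive controlled Grade 2 events give 1 + 1 = 2 holds. Two controlled Grade 3 events give 0 + 0 = 0. The inversion does not depend on how the reduction is read.

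**Dose levels.** Two successive controlled Grade 2 events give 0 + 1 = 1 level, which is 1 of the 2 reductions allowed. A controlled Grade 3 event has two readings:

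- The row writes the reduction only as the step that follows the hold. If waiving the hold waives that step too, the count is 0 levels, and the dose-level rule is inverted as well.
- If the note waives only the hold, the count is 1 level at first occurrence, against 0 for a first Grade 2 event. The dose-level rule is then not inverted.

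**Uncontrolled events.** Grade 2 holds and restarts at the same dose; Grade 3 holds and goes one level lower; Grade 4 stops treatment. The order is correct, so the inversion is confined to controlled events.

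**Whether other text reconciles the rows.**

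- Section 6.3.1 ties dose modification to the worst grade reached, so control by antiemetics does not re-grade the event.
- The recurrence rule in Section 6.3.2 starts from an interruption. It reaches a controlled Grade 2 event, but not a controlled Grade 3 event whose hold was waived.
- Section 6.1.2 only permits antiemetics from Grade 1 upwards.
- Table 6-3 fits the Grade 3 exemption but is silent on Grade 2.

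None of these removes the asymmetry.

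**The case against.** **Grade 4.** A reader might infer that the note flatly contradicts the Grade 4 row. The documents do not support that. The protocol treats interruption and discontinuation as different acts: the title of Section 6.3.2 names both, Section 6.2.6 separates them, and the glossary defines discontinuation as permanent. A condition on interrupting does not cancel an instruction to discontinue. The note's lower bound may simply echo the DLT criterion, which also starts at Grade 3. What remains is that Grade 4 has no interruption step for the note to condition, so including it does no work and blurs a stopping rule.

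**Which row is wrong.** A reader might also infer from Table 6-3 that Grade 2 is the faulty row. The DLT criterion says nothing about managing Grade 2. Table 6-4 uses the same Grade 2 pattern (hold, restart at the same dose, reduce on recurrence) for pancreatitis, creatinine, amylase/lipase and hypertension, so it may be a deliberate template. Removing the Grade 3 exemption would restore the order equally well.

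**Force and duration.** The table is headed as recommendations, and Section 6.3.1 says only that doses may be adjusted. The nausea/vomiting block does not define control. If antiemetics bring a Grade 2 event to Grade 1, the restart condition is met and the hold may be short. These points stand and limit the practical weight, but they do not put the grades in order: the Grade 2 hold is still triggered, and a recurrence still costs a dose level.

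**Conclusion.** The inversion of the hold rule is on the face of the table and nothing elsewhere resolves it: for controlled events, one recommended hold per event at Grade 2 and none at Grade 3. An inversion of dose levels follows only if waiving the Grade 3 hold also waives its reduction, which the note leaves open. The overlap with Grade 4 is an ambiguity worth removing because it touches an unconditional stopping rule.

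Severity is minor. No endpoint, sample size or power figure is affected. Section 14.10.1 states that enrollment is closed, and the Amendment 10 rationale gives 10 patients on treatment (5 dual, 5 triple), which caps the prospective reach. How many patients have had controlled Grade 2 or Grade 3 events is not known from the protocol. The table is still in use, since Amendment 10 itself revised other parts of it.

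**What to change.** 1. In the note, replace '≥ grade 3' with 'Grade 3', so that Grade 4 discontinuation clearly stands.
2. Make the hold rule non-decreasing with grade. Either apply the same condition (not controlled with optimal antiemetics) to the Grade 2 hold, giving controlled events 0 holds at Grades 1 to 3, or remove the Grade 3 exemption, giving 0, 1 and 1. The second option deletes the note and so also settles item 1. The choice relaxes or tightens a safety rule and is the sponsor's medical decision.
3. If the Grade 3 exemption stays, state whether the one-level reduction still applies when the hold is waived.

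The cost is a few words in one block of Table 6-4. Section 12.1 requires a written amendment, so the edit can go with the next one.
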